Estimates of PrEP uptake: PrEP uptake/initiation is defined as the proportion of enrolled women who collect at least one 3-month supply of PrEP. A target sample size of 150 women produces a 95% CI width between 13% (when 70% initiate PrEP) and 15% (when 50% initiate PrEP) (Table 4.) We will calculate the prevalence (and 95% CI) of PrEP initiation using an intercept-only logistic regression model to account for potential clustering within the two groups (women enrolled through partners, women enrolled as individuals). We will describe, compare and test for differences between baseline characteristics of women who do and do not initiate PrEP. Log binomial regression with GEE will be used to estimate univariable and multivariable-adjusted risk ratios (RR) and 95% CIs for the associations between relationship power/social support and PrEP initiation. We will assess potential confounding factors individually; any factor with $P \geq 0.20$ will be excluded from further consideration and the remaining covariates entered into a multivariable model.

Analysis, Aim 2

Hypothesis: 70% of women will have detectable drug 3 months after PrEP initiation.

Estimates of periconception PrEP adherence:

Periconception PrEP adherence will be defined as PrEP initiators with plasma TFV concentration $\geq 40\text{ng/mL}$ three months after initiating PrEP. A target sample size of 105 women initiating PrEP will provide 95% CI width of 18% when

the percent of high adherers is 80% (Table 4). Secondary adherence outcomes are based on Wisepill device monitoring. We will determine the mean and median number of pills taken as well as patterns of adherence (gaps). We will consider Wisepill adherence as a binary outcome defined as taking $\geq 80\%$ of prescribed doses based on biologic plausibility and prior studies [23, 65, 71, 72]. Monthly assessments of median (interquartile range) adherence and number of 72-hour adherence gaps will be used to examine longitudinal trends in adherence.

We will calculate prevalence (and 95%CI) of PrEP adherence using an intercept-only logistic regression model with GEE. Log binomial regression with GEE will be used to estimate univariable and multivariable-adjusted risk ratios (RR) and 95% CIs for the associations between relationship power/social support and PrEP adherence.

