We will use grounded theory methods to analyze interview data. These methods lay out a systematic set of inductive procedures for developing categories of information, organizing data in terms of these categories through coding, connecting the categories, and deriving from these connections an empirically grounded theory[73].

Analysis, Aim 4

Aim 4.1. We will measure prevalence of STIs in up to 150 HIV-negative women who want to conceive a child while at risk for HIV exposure.

Aim 4.2. We will measure six-month incidence of STIs in up to 150 HIV-negative women who conceive or want to conceive a child while at risk for HIV exposure.

Hypothesis 4.2. We expect a higher incidence of condomless sex leading to a higher STI incidence among women who choose PrEP as part of a safer conception strategy compared to women who do not take PrEP.

We intend to evaluate up to 150 HIV-negative women entering the study and estimate the prevalence of any STI and each of the specific STIs. Based on prior work, we anticipate the incidence of any STI will be approximately 35%[74] and that 2 out of 3 women[75] will want to start PrEP. We would have 82% power for a difference of 43% (PrEP group) vs 20% (no PrEP group) using a Chi-square test ($\alpha=0.05$, two-sided).

For Aim 4.1, we will use logistic regression first to test covariates as predictors of having a STI at baseline and then to develop an initial model predicting STI. This model will be applied to the STI incidence data through six months to assess operating characteristics. For Aim 4.2, we will use a logistic regression model predicting incident STIs over six months including PrEP in all models and then adding the number of condomless sex acts to the model. If the number of

condomless sex acts is a significant predictor and there is a substantial reduction in the odds ratio (OR) for PrEP when the number of condomless sex acts is included in the model, then we will conclude that this is a mediator of the PrEP effect.

XV. MONITORING AND QUALITY ASSURANCE

The Ugandan PI will be responsible for continuous data and safety monitoring of all study participants and for alerting the US PI if unexpected concerns arise. Serious adverse events (e.g. physical or emotional injury) will be reported to all involved IRBs according to the guidelines of each IRB (i.e., within ten days for the Partners' IRB) and to Gilead who will be providing study drug.

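### Aim 4.2 judges mediation by the change in the PrEP odds ratio, which at about 35% STI incidence mixes mediation with a scale shift and can hide modest mediation

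*Combined protocol and SAP*

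**What the plan says.** The combined protocol and SAP sets this out in section XIV, Analysis, Aim 4. Hypothesis 4.2 is that women who choose PrEP will have more condomless sex and, through it, more STIs. Incident STI over six months is modelled by logistic regression, "including PrEP in all models and then adding the number of condomless sex acts to the model". Mediation is concluded on two conditions: acts must predict STI significantly, and also "there is a substantial reduction in the odds ratio (OR) for PrEP when the number of condomless sex acts is included in the model". The plan does not say how large a reduction is substantial, and it gives no interval or test for the change.

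The planning figures are in the same section:

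- Sample: "We intend to evaluate up to 150 HIV-negative women entering the study".
- Incidence: "we anticipate the incidence of any STI will be approximately 35" per cent, with two in three women expected to choose PrEP.
- Power: "We would have 82% power for a difference of 43% (PrEP group) vs 20% (no PrEP group"), "using a Chi-square test" at two-sided alpha 0.05.

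Aim 1, in the same section, takes a different effect measure for its common outcome: "Log binomial regression with GEE will be used to estimate univariable and multivariable-adjusted risk ratios (RR"). Aim 2 does the same.

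**The concern.** The rule treats the difference between two ORs, one without acts in the model and one with them, as the part of the PrEP effect that runs through acts. For a common outcome these ORs are on different scales. If acts predict STI, the OR conditional on acts is further from 1 than the crude OR even when acts have the same distribution in both groups. Mediation in the hypothesised direction pulls the OR down while the scale shift pushes it up, and the rule sees only the net result. Because the rule also requires acts to be a significant predictor, it is meant to be applied where the shift exists.

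This rule is the only stated test of the mechanism in hypothesis 4.2. The same mediated share could look like a clear fall in the OR or like no fall, depending on how strongly acts predict STI. The error is present in large samples, so recruiting more women would not remove it.

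**Working it through.** **Inputs from the plan (section XIV, Analysis, Aim 4).** 150 women, two thirds on PrEP (100 vs 50); risks 43% and 20%; two-sided alpha 0.05.

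**The plan's own figures.**
- Overall incidence: (100 × 0.43 + 50 × 0.20)/150 = 53/150 = 35.3%, which matches the stated 35%.
- Null SE: √[0.353 × 0.647 × (1/50 + 1/100)] = 0.0828. Alternative SE: √[0.20 × 0.80/50 + 0.43 × 0.57/100] = 0.0752.
- Power: Φ[(0.23 − 1.96 × 0.0828)/0.0752] = 81.6%. Exact enumeration of the uncorrected chi-square test gives 82.1%. The stated 82% is reproduced.
- Crude OR: (0.43/0.57)/(0.20/0.80) = 3.02.

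**Assumptions that are not in the plan.** Acts M are normal with SD 1 and mean d·PrEP. The model logit P(STI) = a + c·PrEP + b·M is correct, with no interaction and no confounding. The plan does not give the strength exp(b), the OR per SD of acts, so it is varied from 1.5 to 5.

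**Method.** Let λ(p) solve E[expit(λ + bZ)] = p for standard normal Z. Keeping the group risks at 20% and 43% gives:
- adjusted PrEP OR = exp[λ(0.43) − λ(0.20) − b·d];
- mediated share of the risk difference = {0.43 − E[expit(λ(0.43) − b·d + bZ)]}/0.23.

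**Example, OR per SD 2.7.** b = 0.993, λ(0.20) = −1.647, λ(0.43) = −0.340. With no mediation the adjusted OR is exp(1.307) = 3.69, above the crude 3.02. A 20% mediated share needs d = 0.231, so the adjusted OR is exp(1.307 − 0.993 × 0.231) = 2.94, a change of −3%.

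**Change in the PrEP OR from 3.02 when acts are added, by true mediated share.**

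| OR per SD of acts | none (adjusted OR) | 10% | 20% | 30% | 50% |
|---|---|---|---|---|---|
| 1.5 | +4% (3.13) | −6% | −15% | −23% | −38% |
| 1.65 | +6% (3.19) | −4% | −14% | −22% | −37% |
| 2 | +11% (3.35) | 0% | −10% | −19% | −36% |
| 2.7 | +22% (3.69) | +9% | −3% | −14% | −32% |
| 3 | +27% (3.84) | +13% | +0.5% | −11% | −31% |
| 5 | +59% (4.80) | +39% | +21% | +5% | −22% |

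Full mediation gives an adjusted OR of exactly 1 in every row.

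**The same 20% share on the risk-difference scale.** Standardised to the acts of women not on PrEP, the risk difference falls from 0.230 to 0.80 × 0.230 = 0.184 in every row. Standardised to all 150 women, it falls to 0.192–0.193 in every row. Neither result depends materially on how strongly acts predict STI.

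**Trials of 150 women, OR per SD 2.7, 20% mediated.** The OR rule, with a 10% threshold assumed because the plan has none, is met in about 30% of simulated trials. A rule that the bootstrap 95% CI for the change in standardised risk difference excludes zero is met in about 29%. With no mediation the bootstrap rule is met in about 3%.

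**The case against.** The strongest reply is that the problem is confined to weak mediation through a strong predictor. The hypothesis is that condomless sex explains the excess STIs, which implies a sizeable share, and a rule asking for a substantial fall is not designed to flag 10%. This largely stands. For strengths from 1.5 to 3, a 30–50% share lowers the OR by 11–38%, and for a weak predictor (OR per SD 1.5) the shift alone is only 4%. It gives way only for a very strong predictor: at OR per SD 5, a 30% share still shows no fall.

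A second reply is that sample size, not scale, limits what this trial can find. That also stands: the bootstrap rule detects 20% mediation about as rarely as the OR rule. A fixed 10% cut-off on the risk-difference scale would look more sensitive, but mainly because it is looser. With no mediation it is met in about 15–20% of simulated trials, against 1–4% for the OR rule.

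A reader might infer three stronger things that the documents do not support:
- **Adding any strong predictor raises the OR.** This holds for a predictor unrelated to PrEP. Hypothesis 4.2 expects acts to differ by PrEP, and then the net change can go either way.
- **The trial would declare that condomless sex is not a mediator.** The plan says when mediation will be concluded, not what a failed rule means.
- **The powered comparison is affected.** The 43% vs 20% chi-square test does not use this rule.

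**Conclusion.** The concern holds in a limited form. At the plan's own event rates, the change in the PrEP OR is a biased measure of mediation, and the bias runs against finding it. A 20% mediated share appears as anything from a 14% fall to a 0.5% rise as the OR per SD of acts goes from 1.65 to 3, so a modest share can be understated or hidden. Large shares remain visible unless acts predict STI very strongly.

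The sizes rest on assumed acts–STI strengths, normally distributed acts, no interaction and no confounding between acts and STI. The direction of the shift needs only a common outcome and acts that predict it. No error rate can be given for the rule as written, because a substantial reduction is not defined. The point concerns a secondary conclusion and is worth correcting because the correction is cheap.

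**What to change.** Keep the two logistic models. From each, compute the standardised risk difference (or risk ratio) for PrEP, without and with condomless acts, and name the acts distribution used for standardisation. Using that of women not on PrEP makes the change equal the mediated share as defined above; using all women gives a somewhat smaller fall (16–17% for a 20% share). Conclude mediation if the bootstrap 95% CI for the change excludes zero in the hypothesised direction. Report the change with its interval whatever the result, and give the ORs as descriptive results.

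The cost is one SAP sentence and a little more code, with no new data. It brings Aim 4.2 closer to the risk-based measures of Aims 1 and 2. The benefit is a mediated share free of the scale shift and a defined rule. It brings no gain in detection at 150 women, and it does not deal with confounding between acts and STI, which remains an assumption.

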2. We will objectively measure *adherence* to PrEP over up to 9 months. We hypothesize that 70% of women will have detectable plasma drug 3 months after PrEP initiation and that 70% of women will have $>80\%$ adherence by electronic Wisepill monitoring. We hypothesize that women with greater relationship power and social support will be more likely to adhere. We will evaluate adherence to couples-based strategies including delay of condomless sex until partner taking ART for ≥ 3 months and limiting condomless sex to peak fertility. We will measure HIV and pregnancy incidence.
3. Based on a conceptual framework for PrEP adherence, we will conduct in-depth interviews with a subset of up to 45 women and their partners to explore barriers and promoters to use of PrEP and other safer conception strategies.
4. We will offer objective sexually transmitted infection (STI) testing to all participants in order to measure the prevalence, incidence, and factors associated with STIs. We will compare incidence among women who choose and who do not choose PrEP.

Offering women strategies to reduce HIV acquisition risk while meeting reproductive goals provides a unique approach to reducing HIV incidence among women of reproductive age and their children.

III. SUBJECT SELECTION

Self-Report Inclusion Criteria

1. Female
2. Aged 18-35
3. Likely to be fertile based on reproductive health history [55]
4. Reported personal or partner desire to have a child in the next year [56-59]
5. With a partner she reports as HIV-infected or likely to be HIV-infected (e.g. taking medicine daily, goes to clinic routinely, has HIV-infected partners, he has implied that he is “sick” but has not disclosed).
6. Live within 60km of clinic. Not planning on relocating to an area incompatible with ability to attend quarterly clinic over a 9-month follow-up period

Objective Inclusion Criteria

1. HIV-negative (onsite rapid testing)
2. Not currently pregnant (onsite urine b-hcg testing)
3. Fluent in English or local language
4. Otherwise able to participate in the informed consent process

Enrolment Criteria Male Partners

We will enroll a subset of male partners to participate in in-depth interviews. Inclusion criteria include:

1. Partnered with female participant
2. Fluent in English or local language
3. Otherwise able to participate in the informed consent process

Source of Subjects

We will recruit and identify potential participants who may meet our selection criteria from:

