Upon completing the informed consent process, interested participants will be asked to sign or fingerprint a copy of the written informed consent to confirm that they understand the study and what is expected of them as a research participant. A copy of the signed consent form will be given to the participant for their records. After signing of the consent, participants will be considered enrolled as part of the sample goal of 150 uninfected women.

Enrolled women will participate in the outlined mixed-method study to evaluate prevalence and determinants of uptake and adherence (tenofovir plasma concentration >40ng/mL, taking >80% of dispensed pills) to daily, oral TDF/FTC PrEP during periconception among HIV uninfected Ugandan women reporting HIV-infected or unknown serostatus partners. To accomplish this, women will participate in quarterly study visits, HIV and pregnancy testing, questionnaires and safer conception/adherence group counseling sessions. Participants will be eligible to initiate PrEP at any time during the first 6 months of the 9-month (maximum) study follow-up period. Participants will receive a PrEP referral form to bring to the clinic if they chose to initiate PrEP outside of a scheduled study follow up visit.

Women who become pregnant or test positive for HIV during the 9-month follow-up period will complete exit activities (questionnaire and in-depth interview) and be referred to appropriate antenatal and/or HIV follow-up care.

Counseling

Comprehensive safer conception counselling: Enrolled women will be offered a package of safer conception counselling for uninfected women who want to conceive a child with an infected partner:

- Encourage partner testing and serostatus disclosure within the partnership.
- Encourage partner to initiate ART if he is eligible by national guidelines (CD4 cell count \leq 500 or in serodiscordant partnership),
- Delay sex without condoms until he achieves HIV viral load suppression or is on ART x 6 months,
- Consider contraception to delay pregnancy until safer conception strategies implemented
- Limit sex without condoms to peak fertility, and / or
- Consider sperm washing, donor sperm, and adoption as alternatives.

Safer conception counselling will occur at baseline and then quarterly thereafter in non-pregnant women

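### Aim 4.2's rule for concluding that condomless sex mediates a PrEP effect on STIs cannot tell mediation from self-selection into PrEP

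*Combined protocol and SAP*

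**What the plan says.** Aim 4 in Section II is a comparison by choice: "We will compare incidence among women who choose and who do not choose PrEP". Hypothesis 4.2 in Section XIV gives the expected pathway: "We expect a higher incidence of condomless sex leading to a higher STI incidence among women who choose PrEP". The analysis is a logistic model for incident STI over six months, "including PrEP in all models and then adding the number of condomless sex acts to the model". The decision rule has two conditions. The first is that acts reach significance. The second is worded as follows: "there is a substantial reduction in the odds ratio (OR) for PrEP when the number of condomless sex acts". The rule then states its consequence for the case where both conditions hold once that count "is included in the model, then we will conclude that this is a mediator of the PrEP effect".

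On timing, the Overview in Section V says "Participants will be eligible to initiate PrEP at any time during the first 6 months". Under Sexual Behavior in the same section, acts are self-recorded on monthly calendars and reviewed quarterly. Table 2 in Section II lists diary-recorded risk behaviour in the framework of factors thought to influence PrEP initiation and adherence.

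Two other analyses come close to the question. Aim 1 will "describe, compare and test for differences between baseline characteristics of women who do and do not initiate PrEP". Aim 4.1 builds a covariate model for baseline STI, and "This model will be applied to the STI incidence data through six months to assess operating characteristics". Neither is linked to the mediation rule.

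**The concern.** A fall in an exposure's OR when a third variable is added does not show which way the arrows run. The OR falls if PrEP raises condomless sex, which then raises STI risk. It falls in the same way if women who already have more condomless sex are both more likely to choose PrEP and more likely to acquire an STI. Only design or time order can separate the two, and Aim 4.2 specifies neither. PrEP is not randomised, the window for counting acts is not stated, acts before PrEP start are not distinguished from acts after it, and no confounder set is tied to the rule. Table 2 itself allows sexual behaviour to influence PrEP choice, while Aim 4.2 reads the same diary only as a consequence of PrEP.

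At stake is a report that PrEP led to more condomless sex and hence more STIs, when the difference reflects who chose PrEP. Section IX presents the STI work as a step towards designing PrEP programmes, so that message could carry weight.

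**Working it through.** **1. The plan's own figure.** Aim 4 gives 82% power for 43% against 20%, two-sided alpha 0.05. With 150 women and two in three on PrEP, the groups are 100 and 50.
- Pooled proportion: (100 × 0.43 + 50 × 0.20)/150 = 0.353, which matches the stated 35%.
- Null SE: √[0.353 × 0.647 × (1/100 + 1/50)] = 0.0828. Alternative SE: √[0.43 × 0.57/100 + 0.20 × 0.80/50] = 0.0752.
- Power: Φ[(0.23 − 1.96 × 0.0828)/0.0752] = Φ(0.90) = 81.6%.

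The figure reproduces. It covers the crude comparison only and says nothing about the mediation step.

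**2. Inputs for a check of the rule.** From the documents: N = 150, two-thirds on PrEP, 35% incident STI. Assumed, because the documents give no values:
- A woman's underlying level of condomless sex is u ~ N(0,1). Acts are Poisson with log-scale SD 0.6 and mean 8, 12 or 20.
- *Self-selection, no PrEP effect:* logit P(PrEP) = a + βu and logit P(STI) = c + γu, with (β, γ) = (0.5, 0.5) weak, (0.8, 0.6) moderate, (1.0, 0.8) strong. PrEP changes neither acts nor STI.
- *True mediation, no selection:* PrEP is independent of u but raises it by 0.48, 0.72 or 0.85 SD. The acts ratios are exp(0.6 × 0.48) = 1.33, exp(0.6 × 0.72) = 1.54 and exp(0.6 × 0.85) = 1.67. These shifts were chosen to give the same STI contrasts as selection.
- *Rule:* acts P < 0.05 with positive slope, PrEP OR above 1 without acts, and OR with acts ≤ 0.8 × OR without (a 20% fall, since no cut-off is stated). The gated version also requires a significant crude PrEP-STI association.

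**3. Results** (4,000 simulated studies per scenario; ranges are over mean acts).

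| Strength | STI, PrEP vs none | Selection, gated | Mediation, gated | Selection, ungated | Mediation, ungated |
|---|---|---|---|---|---|
| Weak | 36.7 vs 31.6% | about 2% | 1–2% | 14–19% | 14–19% |
| Moderate | 37.9 vs 29.1% | 9–11% | 9–11% | 43–53% | 44–54% |
| Strong | 39.4 vs 26.2% | 27–30% | 29–30% | 76–85% | 79–87% |

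The ORs are as alike as the firing rates. In a separate run of the moderate case, the median PrEP OR went from 1.48–1.49 to 1.12–1.15 under selection and from 1.47–1.50 to 1.11–1.15 under mediation.

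**4. Sensitivity.**
- No selection: 0.3–2% ungated. Negative selection (β = −0.8): 0%.
- Diary error with log-scale SD 0.6, equal to the assumed true spread in acts: under selection, under 1% to 9% gated and about 2% to 27% ungated. Matched mediation gives about 3% to 33% ungated, so the two remain alike.
- A 50% fall required, ungated: 0%, under 1% and 2–7% from weak to strong.

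**5. What would separate the two.** A second model let STI risk depend directly on the acts. Adding acts took the PrEP OR to 0.98–1.02 under either explanation. Replacing acts by a perfectly measured pre-PrEP level gave 0.99–1.05 under selection and 1.76–5.73 under mediation. Time order carries the information. An imperfect proxy helps only in part: in the step 3 model, a baseline measure correlated 0.5 with u, placed in both models, lowers ungated false firing to 6–8%, 21–31% and 47–62%.

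**The case against.** Several points on the other side stand.

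- **The rates rest on assumptions.** The main simulation treats the diary as a nearly error-free measure of the confounder. Realistic error lowers firing a good deal, and so does a stricter cut-off. Error weakens true mediation equally, however, so the rule still does not discriminate.
- **Direction is not established.** The predictors of uptake that the plan hypothesises are greater relationship power and social support, and Section I links limited power to difficulty in negotiating safer sex. Selection could therefore run towards fewer condomless acts, where the rule does not fire.
- **The gated rates may be the fairer ones.** Speaking of a PrEP effect presupposes an association, and that contrast is the powered test. The rule does not state the requirement, so both sets are given.
- **Covariates may not be wholly absent.** The Aim 4.1 model is carried to the six-month data, and the phrase about PrEP being in all models could imply further terms. This is ambiguous; no covariate is named for the rule.

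A reader might infer that the planned 43% against 20% contrast would itself arise from selection, so that the rule would almost always mislead. The documents do not support this: it needs very strong selection, for which they give no evidence. Nor do they show that PrEP leaves condomless sex unchanged. Mediation may be real; the rule cannot establish it.

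**Conclusion.** Wrong as written. The rule draws a causal conclusion from a pattern that self-selection produces equally well, for an exposure that women choose and may start inside the outcome window. This conclusion is structural and needs no simulated rate.

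The size is illustrative only. With no PrEP effect, positive selection and a 20% fall in the OR, the rule is met in about 2% to 30% of studies if a significant crude association is required and about 14% to 85% if not. With diary error as large as the true spread in acts, the ranges are under 1% to 9% and about 2% to 27%. With negative selection it is 0%. Strength and direction of selection, diary accuracy and the cut-off are all absent from the documents, so none of these figures predicts this study's result.

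The point is confined to the mediation conclusion in Aim 4.2. The crude STI comparison and its power statement stand, and the uptake and adherence outcomes are not affected.

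**What to change.** 1. **Core change.** Replace the conclusion that closes the Aim 4.2 rule with: *then the pattern is consistent with mediation or with confounding by sexual behaviour that preceded PrEP choice; both ORs and their change, with confidence intervals, will be reported descriptively.* No decision then hangs on the size of the fall, so neither a cut-off nor a prior significance requirement is needed.
2. **Baseline covariates.** Put in both models a short list, fixed in advance, of measures already collected: for example baseline STI, partner serostatus, risk perception, and the month-0 questionnaire item on delaying condomless sex (Section V, Measures). Keep it short, since only 0.35 × 150 = 52.5, about 53, events are expected. State that this reduces confounding but does not remove it.
3. **Optional sensitivity analysis.** Split diary acts at PrEP start. State two limits: women who start at enrolment have little or no pre-start diary data, and STIs in late starters may precede PrEP, because routine objective tests are at baseline and at month 6 or earlier exit.

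The cost is SAP wording and modest extra analysis on data already collected, a less categorical conclusion, and slightly lower precision.
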